### 5.5.3. Liver Chemistry Stopping Criteria

**Liver chemistry stopping and increased monitoring criteria** have been designed to assure subject safety and evaluate liver event etiology (in alignment with the FDA premarketing clinical liver safety guidance).

<http://www.fda.gov/downloads/Drugs/GuidanceComplianceRegulatoryInformation/Guidances/UCM174090.pdf>

## Phase III-IV Liver Chemistry Stopping and Increased Monitoring Algorithm

Liver chemistry stopping criteria and required follow up assessments are defined in [Appendix 5](#).

### 5.5.3.1. Study Treatment Restart or Rechallenge

Study treatment restart or rechallenge after liver chemistry stopping criteria are met by any subject participating in this study is not allowed.

### 5.5.4. QTc Stopping Criteria

- The *same* QT correction formula *must* be used for *each individual subject* to determine eligibility for and discontinuation from the study. This formula may not be changed or substituted once the subject has been enrolled.
- For example, if a subject is eligible for the protocol based on QTcB, then QTcB must be used for discontinuation of this individual subject as well.
- Once the QT correction formula has been chosen for a subject's eligibility, the *same formula* must continue to be used for that subject *for all QTc data being collected for data analysis*. Safety ECGs and other non-protocol specified ECGs are an exception.
- The QTc should be based on averaged QTc values of triplicate electrocardiograms obtained over a brief (e.g., 5-10 minutes) recording period. For example if a routine ECG demonstrates a prolonged QT, obtain 2 or more ECGs over a brief period and then use the averaged QTc values of the 3 ECGs to determine whether patient should be withdrawn from the study.

A subject who meets either of the bulleted criteria below will be withdrawn from the study:

- QTc > 500 msec OR Uncorrected QT > 600 msec
- [Change from screening (Visit 1) of QTc > 60 msec]

For patients with underlying **bundle branch block**, follow the discontinuation criteria listed below:

Screening (Visit 1) QTc with Bundle Branch Block	Discontinuation QTc with Bundle Branch Block
< 450 msec	> 500 msec
450 – 480 msec	≥ 530 msec

## 5.6. Subject and Study Completion

A subject will be considered to have completed study treatment if he/she receives study treatment at Visit 9 (Week 28) and completes the Exit Visit (Week 32). A subject will be considered to have completed the study if they continue to participate in the study until the Exit Visit assessments have been completed (regardless of whether the subject completed the study treatment schedule).

The end of the study is defined as the last subject's last visit.

## 6. STUDY TREATMENT

### 6.1. Investigational Product and Other Study Treatment

The study treatment and investigational product is mepolizumab (SB-240563), a fully humanised IgG antibody (IgG1, kappa) with human heavy and light chain frameworks. Mepolizumab will be provided as a lyophilised cake in sterile vials for individual use. The vial will be reconstituted with Sterile Water for Injection, just prior to use. Further information on the preparation and administration of study treatment can be found in Section 6.5.

Trade label albuterol/salbutamol metered dose inhalers (MDIs) will be provided locally by each country (except for US sites where GSK Global Supply Organisation will supply the rescue medication) including Sweden where Ventolin Diskus will be used. Subjects will be dispensed a rescue inhaler at the time of screening to be used to primarily treat asthma symptoms on an as needed basis but also during pre and post bronchodilator spirometry assessments (see Section 7.3.2.3.1). The rescue inhaler should be replaced as needed, and collected at the Exit Visit (or Early Withdrawal Visit, as applicable).

## 6.2. Treatment Assignment

This is a single arm open label study. At Visit 2 (Week 0) eligible subjects who meet the continuation to treatment criteria will receive mepolizumab 100mg SC into the upper arm or thigh every 4 weeks over a period of 28 weeks.

A web based interactive system RAMOS NG will be used to dispense mepolizumab from Visit 2 to Visit 9.

## 6.3. Packaging and Labeling

The contents of the label will be in accordance with all applicable regulatory requirements.

## 6.4. Preparation/Handling/Storage/Accountability

- Only subjects enrolled in the study may receive study treatment and only authorized site staff may supply or administer study treatment.
- A description of the methods and materials required for the reconstitution of mepolizumab will be detailed in the staff manual which is available in the Study Reference Manual (SRM).
- Study treatment must be stored in a secure environmentally controlled and monitored (manual or automated) area in accordance with the labelled storage conditions with access limited to the investigator and authorized site staff.
- The investigator, institution, or the head of the medical institution (where applicable) is responsible for study treatment accountability, reconciliation, and record maintenance (i.e. receipt, reconciliation and final disposition records).
- The investigator or designated site staff must document the amount of investigational product administered to study subjects.
- Further guidance and information for final disposition of unused study treatment are provided in the SRM.
- Under normal conditions of handling and administration, study treatment is not expected to pose significant safety risks to site staff. Take adequate precautions to avoid direct eye or skin contact and the generation of aerosols or mists. In the case of unintentional occupational exposure notify the monitor, Medical Monitor and/or GSK study contact.
- A Material Safety Data Sheet (MSDS)/equivalent document describing occupational hazards and recommended handling precautions either will be provided to the investigator, where this is required by local laws, or is available upon request from GSK.

## **6.5. Compliance with Study Treatment Administration**

When subjects are dosed at the site, they will receive study treatment directly from the investigator or designee, under medical supervision. The date and time of each dose administered in the clinic will be recorded in the source documents and reported in the eCRF. The dose of study treatment and study subject identification will be confirmed at the time of dosing by a member of the study site staff other than the person administering the study treatment.

## **6.6. Treatment of Study Treatment Overdose**

The dose of mepolizumab considered to be an overdose has not been defined. There are no known antidotes and GSK does not recommend a specific treatment in the event of a suspected overdose. The investigator will use clinical judgement in treating the symptoms of a suspected overdose.

## **6.7. Treatment after the End of the Study**

The investigator is responsible for ensuring that consideration has been given to the post-study care of the subject's medical condition, whether or not GSK is providing specific post-study treatment.

There are no plans to routinely provide mepolizumab following study completion, as mepolizumab is expected to be commercially available in most countries participating in this study.

## **6.8. Concomitant Medications and Non-Drug Therapies**

### **6.8.1. Permitted Medications and Non-Drug Therapies**

Throughout the study, subjects are to be maintained on their baseline standard of care asthma treatment. The only exception to this is the discontinuation of omalizumab from Visit 2 onwards.

Additional asthma medications such as theophyllines or anti-leukotrienes will be permitted provided that they have been taken regularly in the 3 months prior to first dose of mepolizumab treatment (Visit 2, Week 0).

All concomitant medications taken during the study will be recorded in the eCRF. In addition, all medications taken by the patient for the treatment of asthma including asthma exacerbations in the 12 months prior to Visit 1 must also be recorded in the eCRF. The minimum requirement is that the drug name and the dates of administration are recorded. However, for ICS/LABA, omalizumab and OCS, the dose and regimen (including any change in dose or regimen) must also be recorded. Continuous Positive Airway Pressure (CPAP) for the treatment of obstructive sleep apnea is permitted, if initiated prior to the Screening Visit 1.

### 6.8.2. Prohibited Medications and Non-Drug Therapies

The following medications are not allowed prior to screening (Visit 1), according to the following schedule, or during the study:

**Table 4 Medications not allowed prior to the Screening Visit and throughout the study**

Medication	Washout Time Prior to Screening Visit
Investigational drugs	1 month or 5 half-lives whichever is longer
Monoclonal antibodies**	5 half-lives
Experimental anti-inflammatory drugs (non biologicals)	3 months
Immunosuppressive medications such as those listed below (not all inclusive)	

 
Regular systemic (oral or parenteral) corticosteroids for the treatment of conditions other than asthma. Long-acting depot corticosteroids if used to treat a condition other than asthma
 
Methotrexate, troleandomycin, cyclosporin, azathioprine
 
Oral gold
 
Chemotherapy used for conditions other than asthma
 
	3 months 1 month 3 months 12 months

\*\*= Omalizumab is permitted during screening and run-in but must be discontinued at Visit 2.

Additionally, Bronchial Thermoplasty and Radiotherapy are excluded for 12 months prior to Visit 1 and throughout the study. Neither CPAP nor oxygen therapy may be initiated on or after Visit 1.

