## 4. STUDY DESIGN

### 4.1. Overall Design

The study will be a multi-centre, open-label single arm trial. Patients with severe eosinophilic asthma who are receiving omalizumab, but are not optimally controlled will be eligible to participate and will be identified through the ACQ-5 with a screening (Visit 1) and baseline (Visit 2) score of  $\geq 1.5$  and a history of  $\geq 2$  exacerbations in the past 12 months. For those subjects receiving omalizumab for  $\geq 8$  months, at least 1 exacerbation must be while on omalizumab treatment.

Subjects meeting all the inclusion/exclusion criteria at screening Visit 1, will enter a run-in period for a minimum of one week and up to 4 weeks to assess subjects' eligibility and compliance with study-related procedures.

[figure not shown]
Subjects will remain on their current maintenance therapy throughout the run-in period, including omalizumab. At Visit 2 subjects will discontinue omalizumab treatment and be switched to mepolizumab 100 mg SC every 4 weeks. Except for omalizumab, subjects will remain on their current maintenance therapy throughout the open-label treatment period.

Every subject, including those who withdraw early from the study, will be asked to return for an Exit Visit approximately 4 weeks after their last dose of study treatment.

An Exit interview will be conducted during the Exit Visit or early withdrawal Visit in a subset of participating sites and in a subset of patient who consent to participate.

The investigator is responsible for ensuring that consideration has been given to the post-study care of the patient's medical condition. At the end of the study, subjects may be prescribed appropriate alternative asthma therapy if needed and as determined by the study Investigator.

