## 5.5. Withdrawal/Stopping Criteria

### 5.5.1. Withdrawal from Study Treatment

Subjects may be withdrawn from study treatment at any time by the Investigator if it is considered to be detrimental for them to continue in the study. Reasons for withdrawal from study treatment can include: an adverse event (including abnormal liver function test or abnormal laboratory results), clinically significant abnormality identified on ECG, lost to follow-up, protocol violation, lack of efficacy, sponsor terminated study, non-compliance, continued in error, pregnancy, or for any other reason.

Subjects who have permanently withdrawn mepolizumab study treatment are not required to withdraw from the study. Every effort should be made to complete all remaining protocol specified visits even if they have discontinued mepolizumab treatment provided there are no safety concerns with doing so.

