### 5.5.2. Withdrawal from the Study

A subject may withdraw from study at any time at his/her own request, or may be withdrawn at any time at the discretion of the investigator for safety, behavioural or administrative reasons. If a subject withdraws from the study, he/she may request destruction of any samples taken, and the investigator must document this in the site study records.

A reason for the withdrawal from the study must be captured in the eCRF.

A subject will also be withdrawn from the study, in consultation with the medical monitor and principal investigator, if any of the following stopping criteria are met:

- Laboratory parameters: Clinically important changes in laboratory parameters identified
- ECG: Clinically significant abnormality identified during the study that meet the QTc stopping criteria described in Section 5.5.4.
- Liver Chemistry: Meets any of the Liver chemistry stopping criteria (See Section 5.5.3 and [Appendix 5](#))
- Pregnancy: Positive pregnancy test (see [Appendix 3](#))

The following actions must be taken in relation to a subject who fails to attend the clinic for a required study visit:

[figure not shown]
- The site must attempt to contact the subject and re-schedule the missed visit as soon as possible.
- The site must counsel the subject on the importance of maintaining the assigned visit schedule and ascertain whether or not the subject wishes to and/or should continue in the study.
- In cases where the subject is deemed 'lost to follow up', the investigator or designee must make every effort to regain contact with the subject (where possible, 3 telephone calls and if necessary a certified letter to the subject's last known mailing address or local equivalent methods). These contact attempts should be documented in the subject's medical record.
- Should the subject continue to be unreachable, only then will he/she be considered to have withdrawn from the study with a primary reason of "Lost to Follow-up".

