10.4.4. Treatment Phases (Concomitant Medications)

Concomitant medications will be classified according to time of occurrence relative to the first and last date of the study treatment.

Treatment/Study Phase	Definition
Taken Before the Run-in	If Con-med Start Date < Date of Visit 1
Taken During the Run-in	
 • If Con-med Start Date < Date of Visit 1 and Con-med Stop Date ≤ Date of Visit 1, or • If Date of Visit 1 ≤ Con-med Start Date < First dose of mepolizumab
Taken During Treatment	
 • If Con-med Start Date < First dose of mepolizumab and Con-med Stop Date ≥ First dose of mepolizumab or • If First dose of mepolizumab ≤ Con-med Start Date ≤ Last dose of mepolizumab + 28 days • If the con-med start or stop date is missing or partial then the con-med will be considered on-treatment unless there is evidence to the contrary (e.g. month/year of con-med stop date is present and is before the month/year of the first dose of mepolizumab).
Started During Treatment	Subset of con-meds Taken During Treatment for which: First dose of mepolizumab ≤ Con-med Start Date ≤ Last dose of mepolizumab + 28 days
Taken Post Treatment	
 • Last dose of mepolizumab + 28 days < Con-med Stop Date

A medication will be summarised in every treatment/study phase in which it was taken,

so for example a medication that was started in the run-in and stopped during treatment will appear in both the during the run-in and during treatment tables.

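### SAP 10.4.4 leaves ongoing medicines out of the post-treatment phase and reverses a run-in rule; the protocol does not say whether medication restrictions outlast mepolizumab

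*Protocol*

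**What the plan says.** **SAP 10.4.4 (concomitant medications).**
- *Taken Post Treatment* has one condition: "Last dose of mepolizumab + 28 days < Con-med Stop Date".
- *Taken During the Run-in* has two alternative lines. The first is "If Con-med Start Date < Date of Visit 1 and Con-med Stop Date ≤ Date of Visit 1, or". The second takes medicines started from Visit 1 up to the first dose.
- *Taken During Treatment* takes medicines started before the first dose and stopped on or after it, or started between the first dose and last dose + 28 days. A missing or partial start or stop date puts the medicine on-treatment by default, unless something shows otherwise.
- The section closes by stating that a medicine counts in each phase in which the subject took it.

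Table 1.23 in SAP 10.13.1.1 summarises asthma medicines taken post-treatment in the ITT population.

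**Primary analysis.** SAP 7.1.2 keeps every ACQ-5 value up to Week 32, including values recorded after mepolizumab was stopped.

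**Protocol.** On retention, Section 5.5.1 says: "Subjects who have permanently withdrawn mepolizumab study treatment are not required to withdraw from the study". On background therapy, Section 6.8.1 says: "Throughout the study, subjects are to be maintained on their baseline standard of care asthma treatment". Table 4 in Section 6.8.2, which includes monoclonal antibodies, is titled "Medications not allowed prior to the Screening Visit and throughout the study"; its only exception is omalizumab before Visit 2. Section 4.1 uses a different time frame, "Except for omalizumab, subjects will remain on their current maintenance therapy throughout the open-label treatment period", and places other treatment later: "At the end of the study, subjects may be prescribed appropriate alternative asthma therapy if needed".

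**The concern.** The phase rules determine what a reader can learn about therapy taken after mepolizumab was stopped. A replacement therapy is likely to be still in use at the end of the study, so a post-treatment rule that needs a stop date tends to miss the medicines of most interest.

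This matters because the ITT estimate includes ACQ-5 values recorded off mepolizumab, and the SAP has no rule for values recorded after another biologic is started. A reader of the Week 32 change would want to know how many such values it contains.

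The protocol adds uncertainty. Subjects off mepolizumab are encouraged to stay, but the sections on permitted and prohibited medication do not say whether they still bind those subjects.

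**Working it through.** **1. Applying the SAP 10.4.4 rules.** Take Visit 1 on day −14, first dose on day 1 and last dose on day 85. The post-treatment cut-off is 85 + 28 = day 113. *Ongoing* is taken to mean a blank stop date. The third column is what the section's closing principle requires.

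| Medicine | Phases under the inequalities alone | Phases in which it was taken |
|---|---|---|
| Start day 120, stop day 150 | post | post |
| Start day 120, ongoing | none | post |
| Start day 100, ongoing | during | during, post |
| Start day 100, stop day 150 | during, post | during, post |
| Start day −400, ongoing | before run-in | before run-in, run-in, during, post |
| Start day −400, stop day 150 | before run-in, during, post | before run-in, run-in, during, post |

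**2. Adding the missing-date default.** The default places the day −400 ongoing medicine in *during*. For the day 120 ongoing medicine there are two readings. Either the default puts it in *during*, which is the wrong phase, or its start date counts as contrary evidence and it stays in no phase. No reading puts any of the three ongoing medicines in *post*, so all three are absent from Table 1.23. SAP 10.7.2.1 does not help, because for concomitant medications it imputes partial dates only.

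**3. The run-in line.** Requiring a stop on or before Visit 1 selects medicines that ended before run-in began. A maintenance controller started long before Visit 1 and continued through run-in fails that line. It also fails the second line, because it did not start after Visit 1. The last two rows of the table show this.

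**4. Where the phases are used.** Table 1.23 uses the post-treatment phase. Tables 1.20 to 1.24 include no table of medicines taken during run-in, and Table 1.21 selects on starting before the first dose. The run-in error therefore changes classification but no listed display.

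**5. ACQ-5 after a switch.** SAP Table 5 plans on-treatment analyses for blood eosinophils and for clinically significant exacerbations. SAP Table 4 plans ACQ-5 on on- and off-treatment data together only.

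**6. Scale, on assumed inputs.** The protocol's own figures reproduce. With 120 × 0.85 = 102 subjects, SE = 0.96/√102 = 0.0951. The critical change is −0.55 − 1.96 × 0.0951 = −0.736 (stated −0.74). Power at −0.86 is Φ(0.31/0.0951 − 1.96) = Φ(1.30) = 90.3% (stated 90%). These figures are not in dispute.

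If a share f of Week 32 values comes from switched subjects with an extra change x, the mean moves by f × x:
- f = 5%, x = −0.34: 0.05 × (−0.34) = −0.017.
- f = 15%, x = −1.0: 0.15 × (−1.0) = −0.15.

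The distance from the assumed true change to the critical change is 0.86 − 0.74 = 0.12. The low end is negligible and the high end is not. The documents give neither f nor x, so this supports counting the switches. It is not evidence of bias.

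**7. The protocol passages side by side.** Section 6.8.1 and Table 4 run for the whole study. Section 4.1 ties maintenance therapy to the open-label treatment period and mentions other therapy only at the end of the study. Section 5.5.1 creates a group that is off treatment but still in the study. None of the four says which time frame applies to that group. The per-protocol exclusions in SAP 10.1.1 show the same split: number 14 (prohibited medication) covers the whole study, while number 13 (ICS or controller changes) covers open-label treatment only.

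**The case against.** The best defence is that the closing principle of SAP 10.4.4 governs and the inequalities are shorthand. A programmer would include ongoing medicines, and the run-in sign is a slip that touches no table. The documents also do not say that *ongoing* is stored as a blank stop date. All of this is fair as to intent. But the inequalities are the operative specification, and as written they disagree with the stated intent.

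A second defence concerns visibility. A reader might infer that a switch to another biologic would escape notice. The documents do not support that:
- Protocol 6.8.1 has all concomitant medications recorded in the eCRF.
- Use of a prohibited medicine is per-protocol exclusion 14.
- Important deviations are summarised and listed (Table 1.25, Listing 8), and Listing 8 includes per-protocol exclusions.
- A per-protocol analysis of the primary endpoint is planned.

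This defence largely stands. What remains is narrower. The listings contain no subject-level listing of concomitant medications, exclusion 13 does not reach controller changes after open-label treatment, and no planned display counts post-switch values in the ITT estimate. The only per-protocol ACQ-5 table in the display list, Table 2.3, is a responder table.

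A third defence is that the protocol passages can all be obeyed at once: a subject may stop mepolizumab, attend the remaining visits and take no other biologic. That is correct, so this is a lack of clarity and not a strict contradiction.

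**Conclusion.** Minor. The two SAP 10.4.4 lines are wrong as written. The first affects Table 1.23, provided that ongoing medicines carry no stop date. The second affects phase classification only. Neither is shown to change an efficacy estimate. The protocol passages leave open whether the medication restrictions continue after mepolizumab is stopped.

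Two stronger conclusions should not be drawn.
- A reader might infer that the restrictions force subjects out and so make Week 32 data missing. Section 5.5.2 introduces its mandatory criteria with "A subject will also be withdrawn from the study, in consultation with the medical monitor and principal investigator, if any of the following stopping criteria" and then lists laboratory, ECG, liver and pregnancy findings. Prohibited medication is not among them, and Section 5.5.1 names protocol violation only as a possible reason for stopping study treatment. Section 7 bars waivers but does not require removal.
- A reader might take the planned 15% of 120, or 18 subjects, as the number affected. Protocol 9.2.1 defines that 15% as subjects who leave the study and lack Week 32 data. The group at issue stops mepolizumab and stays, and the documents give no number for it.

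**What to change.** **SAP 10.4.4.**
- Define *Taken Post Treatment* as a stop date after last dose + 28 days, or ongoing/missing stop date.
- Change the first run-in line so that it requires a stop date on or after Visit 1, or ongoing.
- State how ongoing medicines are recorded, and that a start date after last dose + 28 days overrides the on-treatment default.

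**SAP 7.1.2.** From the recorded start dates, report how many Week 32 ACQ-5 values in the ITT estimate follow the start of another biologic, as a supplement to the planned per-protocol analysis.

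**Protocol.** Reconcile Sections 4.1, 5.5.1, 6.8.1 and Table 4 so that they say whether the medication restrictions continue for subjects who have stopped mepolizumab but remain in the study. The sponsor's clinical team decides how.

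**Cost.** A few SAP lines, one count and a protocol clarification. No new data are needed, because Section 6.8.1 already has all concomitant medications recorded with their dates of administration.
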